**Statistical Analysis Plan**

Catalyst Biosciences, Inc. Protocol # MAA-201

**Version 2.0**

**Syneos Health #1009647**

	Hr 12	Part 1b, Hr 36	2130 - 2190 min
	Hr 24	Part 1b, Hr 48	2790 - 2970 min
	Hr 30	Part 1b, Hr 54	3150 - 3330 min
	Hr 48	Part 1b, Hr 72	4230 - 4410 min
Part 2	Day 3	Part 2, Day 6	6 - 7 days
	Day 5	Part 2, Day 8	8 - 9 days
	Day 7	Part 2, Day 10	10 - 11 days
	Day 14	Part 2, Day 17	15 - 19 days
	Day 21	Part 2, Day 24	22 - 26 days
	Day 28	Part 2, Day 31	29 - 33 days
	Day 42	Part 2, Day 45	42 - 48 days
	Day 50	Part 2, Day 53	53 - 56 days

Statistical Analysis Plan

Catalyst Biosciences, Inc. Protocol # MAA-201

Version 2.0

Syneos Health #1009647

## 7. DEMOGRAPHIC, OTHER BASELINE CHARACTERISTICS AND MEDICATION

### 7.1 SUBJECT DISPOSITION AND WITHDRAWALS

Subject disposition will be summarized overall and presented for the number and percentage of subjects for the following (a consort diagram can be found in [Appendix Y](#)):

- Screened subject (only number of subjects will be presented)
- Screen failure
- Enrolled subjects
- Safety population
- ITT population
- Modified ITT population
- Per protocol population
- Subjects who completed the treatment
- Subjects who discontinued the treatment and the reason for discontinuation
- Subjects who completed for each study part (Part 1a, Part 1b, and Part 2)
- Subjects who discontinued for each study part (Part 1a, Part 1b and Part 2)
- Subjects who completed the study
- Subjects who discontinued the study and the reason for discontinuations

### 7.2 DEMOGRAPHIC AND OTHER BASELINE CHARACTERISTICS

Descriptive statistics will be presented for demographic and baseline characteristics using the safety populations. Demographic and baseline characteristics, including age, gender, race, ethnicity, height, weight, and body mass index (BMI), will be summarized overall and listed.

The below conversions will be used to calculate BMI:

Height (in cm) = height (in inches) \* 2.54

Weight (in kg) = weight (in lbs) \* 0.4536

**Statistical Analysis Plan**

Catalyst Biosciences, Inc. Protocol # MAA-201

Version 2.0

Syneos Health #1009647

$$\text{BMI (kg/m}^2\text{)} = \text{Weight (kg)} / [\text{Height (m)}^2]$$

### 7.3 MEDICAL HISTORY

The medical history of subjects will be coded by system organ class (SOC) and preferred term (PT) using Medical Dictionary for Regulatory Activities (MedDRA) version 20.1. The number and percentage of subjects with medical history will be summarized overall presenting the number and percentage of subjects with a history in each SOC and in each preferred term (PT) for the safety population.

### 7.4 HEMOPHILIA HISTORY

Hemophilia history will be summarized overall for the categories below:

- Number and percentage of hemophilia type (Hemophilia A and Hemophilia B)
- Age at diagnosis
- Number and percentage of clinical setting of hemophilia diagnosis (Prenatal, at birth and unanticipated/unexpected bleeding)
- Factor VIII level
- Factor IX level
- Number and percentage of clinical setting of diagnosis of inhibitor (Incidental laboratory finding, non-responsiveness to factor infusion and other)
- Number and percentage of history of orthopedic procedure (Yes and No)
- Number and percentage of types of orthopedic procedure (Joint aspiration, synovectomy, fusion, joint replacements and other)

### 7.5 HEMOPHILIA BLEED HISTORY

The frequency of hemophilia bleed history will be summarized descriptively for the prior 6 months and the prior 50 days respectively.

Individual plot to show the bleeding pattern will be presented for each subject by the time the bleeding starts and ends.

Hemophilia bleed history and other hemophilia history will be listed.

### 7.6 CONCOMITANT MEDICATION

The number and percentage of subjects using each concomitant medication will be summarized overall according to the World Health Organization Drug Dictionary

**Statistical Analysis Plan**

Catalyst Biosciences, Inc. Protocol # MAA-201

**Version 2.0**

**Syneos Health #1009647**

(WHODRUG) Global B3 Sept 2017 for the safety population. Anatomical Therapeutic Chemical (ATC) level III and PT will be used. Subjects with multiple uses of a concomitant medication will be counted only once for a given PT in a given ATC level III term and only once within a given ATC level III term.

The number and percentage of subjects using each hemophilia specific medication will be summarized separately.

Statistical Analysis Plan

Catalyst Biosciences, Inc. Protocol # MAA-201

Version 2.0

Syneos Health #1009647

## 8. EFFICACY

Efficacy analyses will be based on the ITT, modified ITT and per-protocol population and summarized by study part, final dose level and overall.

The primary efficacy endpoint will be tested inferentially using a one-sided test with 2.5% significance level. All other statistical tests will be performed at the 0.05 significance level using two-sided tests (i.e. two-sided 95% CIs).

### 8.1 PRIMARY EFFICACY ENDPOINT AND ANALYSIS

#### 8.1.1 Primary Efficacy Endpoint

The analysis of the primary endpoint (annualized bleeding rate (ABR) for spontaneous and traumatic bleeds) under the final treated dose of MarzAA for each subject will be based on the one sample test compared to a pre-defined rate assumed for the on-demand therapy. The pre-defined rate is assumed to be 12 bleeds in total (i.e. one bleed per month), defined as the minimum ABR for each subject according to inclusion criterion 2 (defined as the null hypothesis (H0)). The comparison of the actual ABR for MarzAA at the highest dose for an individual will be performed using the one-sample test for a Poisson rate versus the pre-defined margin of 12 (using an exact Poisson regression model in SAS 9.4). A one-tailed 2.5% significance level will be used For the following hypothesis test:

$$H_0: ABR_{\text{MarzAA}} \geq 12 \text{ versus } H_1: ABR_{\text{MarzAA}} < 12.$$

The ITT population will be used for the statistical analysis of the primary efficacy endpoint.

In order to calculate the ABR for subjects who do not have a total of 12 months of follow up, the ABR will be calculated as:

$$(\text{Number of bleeds/number of months on study}) \times 12$$

Note: number of months is calculated as the exposure (in days) at each dose level / 30.5.

Formally, assume that the hypothesis is: H0:  $\lambda = \lambda_0$  vs Ha:  $\lambda < \lambda_0$ . Let n be the number of subjects, we can calculate the critical point Ncrit which is the largest integer meeting

$$\sum_0^{N_{crit}} e^{-n\lambda_0} \frac{(n\lambda_0)^k}{k!} \leq \alpha \quad (1)$$

If the total number of bleeds during the final MarzAA dose for all subjects is less than Ncrit, then the null hypothesis is rejected.

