4.2 END OF STUDY DEFINITION

The minimum duration of treatment for each subject is approximately 2 months (if no dose escalation is required) and the maximum duration is approximately 7 months (if three dose escalations are required).

Up to 4 weeks for screening period; 24 hours for the part 1a (single IV dosing and PK/PD/Safety testing); 48 hours for the Part 1b (single SC dosing and PK/PD/safety testing); and up to 197 days of daily SC dosing and a PK/PD/safety follow-up assessment 30 days after last dose. Subjects must have no spontaneous bleeding for 50 days if on the first three dose levels or complete 50 days of treatment on the fourth dose level. The end of study visit will be 30 days after the last dose of study drug treatment in Part 2.

A participant is considered to have completed the study if he has completed all phases of the study, including treatment at the same dose level for 50 days, and returned for procedures listed under end of study visit as shown in the SOA.

MAA-201 VERSION 2.0

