6.1.2.1 Guidelines for Dose Escalation

An escalation to the next dose level is required if a spontaneous bleeding event occurs after the fifth daily dose on a dose level. A dose escalation will not occur if the subject is on the maximum dose level of 120 µg/kg. A spontaneous bleeding episode is defined as one that is precipitated by normal activities of daily living (ADL). Subjects will use their current bypass regimen for any spontaneous or traumatic bleed that occurs while on study drug.

Three dose escalations are allowed during Part 2: 60, 90, and 120 µg/kg (maximum dose).

Safety parameters and PK/PD assessments at each dose level will be monitored to ensure that dose escalation to a higher dose level is appropriate.

The spontaneous bleeding episode must be reported to the clinical team immediately and determination of a dose escalation will be made on review of available clinical information related to the spontaneous bleeding episode and may require subsequent treatment and laboratory data, including available results from the PK/PD/safety assessments.

A decision to proceed with dose escalation will be made by the principal investigator in agreement with personnel who have Sponsor, or designee, medical oversight responsibility.

If there is disagreement amongst any of those individuals, the decision will be reviewed on an urgent basis by an independent Medical Consultant for Safety Oversight.

MAA-201 VERSION 2.0

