6.4 STUDY INTERVENTION COMPLIANCE

Reasonable efforts should be made to ensure that study drug administration is administered daily in the morning. However, if an unavoidable disruption of the daily administration occurs and a dose is not administered then the subject should be instructed to continue beginning the following day in the morning.

If the subject misses two or more daily doses, then a spontaneous bleeding event will result in a dose escalation only if it occurs 4 days or longer after resumption of the daily administration.

MAA-201 VERSION 2.0

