7.2 PARTICIPANT DISCONTINUATION/WITHDRAWAL FROM THE STUDY

Subjects are free to withdraw from participation in the study at any time upon request.

MAA-201 VERSION 2.0

An investigator may discontinue or withdraw a participant from the study for the following reasons:

- Significant study intervention non-compliance
- If any clinical AE, laboratory abnormality, or other medical condition or situation occurs such that continued participation in the study would not be in the best interest of the participant
- If the participant meets a criterion (either newly developed or not previously recognized) that precludes further study participation
- Decision by Investigator or Sponsor

The reason for participant discontinuation or withdrawal from the study and the date will be recorded on the electronic case report form (eCRF).

Replacement of a subject occurs for the following reason:

- If a subject does not complete the study as defined in the protocol (ie, before receiving study drug for 50 days at the same dose level), another subject will need to be enrolled.

If the subject withdraws from the study and also withdraws consent for disclosure of future information, no further evaluations should be performed, and no additional data should be collected. The sponsor may retain and continue to use any data collected before such withdrawal of consent.

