9.1 STUDY HYPOTHESIS

The null hypothesis (H0) is that the ABR in all subjects treated with daily SC administration of MarzAA will result in an ABR of 12 as compared to the historical control rate of 12, i.e. H0: ABR (for MarzAA) = 12. The alternative hypothesis (H1): ABR (for MarzAA) < 12.

Primary Endpoint

The primary endpoint will include:

- ABR (spontaneous and total) during Part 2 when on final MarzAA dose level versus recorded historical ABR

Bleeding events will be evaluated as follows:

- Spontaneous vs Traumatic

A spontaneous bleeding episode is defined as one that is precipitated by normal ADL.

MAA-201 VERSION 2.0

Secondary Endpoints

The secondary endpoints will include:

- Occurrence of breakthrough bleeds requiring escalation to higher dose level.
- Safety parameters: Occurrence of clinical thrombotic event not attributable to another cause, and occurrence of antibody formation resulting in a decreased endogenous level of FVII or FVIIa.
- Change in coagulation parameters (PT, aPTT, fibrinogen, MarzAA antigen and activity levels, and TGT) from pre-dose.
- Occurrence of an antibody response to MarzAA and whether it is inhibitory and cross-reactive to wt-rFVIIa or wt-FVII.
- Clinically significant levels of thrombogenicity markers resulting from daily SC administration of MarzAA
- Feasibility and ease of use of daily SC self-administration by patient as measured by compliance with treatment
- Breakthrough bleeding events will be categorized as follows:
 - Number of bleeds that are life threatening
 - Number that require hospitalization and/or blood transfusion
 - Number of muscle bleeds
 - Median time to resolution (and interquartile range) of bleeds

Exploratory Endpoints

- Identification of biomarker(s) such as antigen levels, activity levels, or global thrombosis assay evaluation that can be used to predict or correlate with a subject's lack of spontaneous bleeding.
- Identification of biomarker(s) such as D-dimer, F1+2, or a functional assay of the FVIIa activity that will identify or predict clinical thrombogenicity with the daily SC administration of MarzAA.
- Identification of biomarker(s) such as D-dimer, F1+2, or a functional assay of the FVIIa activity that will identify or predict clinical thrombogenicity of daily SC administration of MarzAA when use of rescue medication is required.
- PRO measures: EQ-5D, VAS; Haem-A-QoL; Hemophilia Activities List (HAL)

MAA-201 VERSION 2.0

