9.4.2 Analysis of the Primary Efficacy Endpoint(s)

The analysis of the primary endpoint (annualized bleeding rate) of the final dose used to treat a subject will be based on the evaluation of the ABR of MarzAA compared to a rate seen with on-demand therapy. The latter is assumed to be 12 (or one bleed per month) as our null hypothesis (H0). The comparison of the actual ABR for MarzAA either pooled across all doses used or evaluated at the highest dose for an individual will be compared to this null hypothesized value using the one-sample test for a Poisson rate (using an exact calculation of the p-value based on the program StatXact 11, Cytel, Inc., 2015). Because this will be a one-tailed test (the alternative hypothesis is the ABR for MarzAA will be < 12), a one-tailed 2.5% significance level will be used.

To calculate the ABR for subjects who do not have a total of 12 months of follow up, the ABR will be calculated as:

$$(\text{number of bleeds/number of months on study}) \times 12$$

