**3.4 SUBJECT SELECTION**

**3.4.1 Inclusion Criteria**

1. Confirmed diagnosis of severe congenital hemophilia A or B with an inhibitor.
2. History of frequent spontaneous bleeding episodes (historical annualized bleeding rate [ABR] of  $\geq 12$ ).
3. Male, age 18 or older.
4. Agreement to use highly effective birth control throughout the study.
5. Affirmation of informed consent with signature confirmation before any trial-related activities. (Trial related activities are any procedure that would not have been performed during normal clinical management of the subject).
6. Stated willingness to comply with all study procedures and availability for the duration of the study.

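### The primary test counts bleeds only at the final dose level, which the escalation rule selects for having few bleeds; if the triggering bleed stays at the old level, the 2.5% error rate fails at the SAP's own null of 12

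*SAP*

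**What the plan says.** The endpoint in Protocol 9.1 is "ABR (spontaneous and total) during Part 2 when on final MarzAA dose level versus recorded historical ABR". Protocol 9.4.2 lets the comparison with 12 be "either pooled across all doses used or evaluated at the highest dose for an individual". SAP 8.1.1 keeps only the second option: "The comparison of the actual ABR for MarzAA at the highest dose for an individual will be performed using the one-sample test". It sets the null at 12 bleeds in total and counts spontaneous and traumatic bleeds during the final dose. SAP section 14 declares only a change of software.

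Two protocol rules decide which level is final. Section 6.1.2.1: "An escalation to the next dose level is required if a spontaneous bleeding event occurs after the fifth daily dose on a dose level". Section 4.2: "Subjects must have no spontaneous bleeding for 50 days if on the first three dose levels". At 120 µg/kg the subject stays for 50 days whatever happens.

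Protocol 8.2.6 and the note to Table 4 in section 1.3 call the day of the bleed Day 0 of a reset count and start the new dose on the following day. Neither document says to which dose level the triggering bleed belongs in the ABR.

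**The concern.** The outcome chooses its own measurement window. A late spontaneous bleed at 30, 60 or 90 µg/kg moves the subject up and leaves that bleed in a level the test discards. The 50 days that qualify a lower level as final are the same days that then estimate its rate.

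Some bleeds do still count at the final level:
- spontaneous bleeds before the fifth dose;
- traumatic bleeds;
- bleeds soon after two or more missed doses, since Protocol 6.4 allows "a dose escalation only if it occurs 4 days or longer after resumption";
- bleeds for which escalation is not agreed;
- every bleed at 120 µg/kg;
- bleeds in ITT subjects who leave early.

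These soften the selection but do not remove it. At stake is whether the only one-sided 2.5% test in a single-arm, open-label trial can separate an active product from an inert one, and whether the reported ABR describes the subjects' bleeding.

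**Working it through.** **Inputs.** 12 subjects, null 12, alternative 6 (SAP 3.5). One-sided 2.5%, and a month of 30.5 days, so a year of 12 × 30.5 = 366 days (SAP 8.1.1). Four levels, a five-dose grace period and 50 days at the final level (Protocol 4.2, 6.1.2). The documents do not give the spontaneous share of bleeds; it is assumed and varied.

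**1. The plan's own power.** With one full year per subject, 12 subjects give a null mean of 144, a critical count of 120 and power near 100%. Six subjects give 72, 55 and 99.9%. SAP 3.5 reproduces, but only with a year of follow-up each.

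**2. Correcting exposure.** Final-dose exposure is 12 × 50 / 366 = 1.64 years, so 12 × 1.64 = 19.7 bleeds are expected at the null. P(≤ 11) = 0.0251 just misses 2.5%, so the critical count is 10. Power at a rate of 6, ignoring escalation, is about 60%. The steps below use this corrected test. Equation (1) as printed has no exposure term (n × λ0 = 144) and would reject in all of these trials; that is a separate error.

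**3. Expected final-dose ABR with no drug effect.** Let s be the spontaneous and t the traumatic rate per year, with the triggering bleed counted at the old level.
- Chance of no late spontaneous bleed at a level: p = exp(−s × 45/366)
- Chance that the final level is below 120 µg/kg: q = 1 − (1 − p)³
- ABR = q × 0.1s + (1 − q) × s + t, where 0.1 = 5/50 is the grace period

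For s = 12, t = 0: p = exp(−1.475) = 0.229; q = 1 − 0.771³ = 0.541; ABR = 0.541 × 1.2 + 0.459 × 12 = 6.16.

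**4. Rejection.** 40,000 simulated trials of 12 subjects, constant rates, no drug effect, no withdrawals:

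| True rate (spontaneous + traumatic) | Final-dose ABR | Rejection |
|---|---|---|
| 12 + 0 | 6.2 | 57% |
| 9 + 3 | 6.3 | 54% |
| 6 + 6 | 7.4 | 34-35% |
| 4.8 + 7.2 | 8.1 | 24% |
| 12 + 2 | 8.2 | 27% |
| 12 + 4 | 10.2 | 9% |
| 12 + 6 | 12.2 | 2% |
| 18 + 0 | 13.2 | 2% |

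Pooling all Part 2 bleeds and exposure in the same simulation, at a true total of 12, gives an ABR of 12.0 and rejection of 2.0-2.3%. The final-dose restriction is therefore the cause.

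**5. Sensitivity at a true total of 12, 50-100% spontaneous.**
- A 365-day year moves the critical count to 11: rejection 45-67%.
- The SAP's strict wording (reject only below N_crit): 24-47%.
- Triggering bleed counted at the *new* level: ABR 11.8, 11.2 and 11.2 for the first three rows, rejection about 2%.

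**The case against.** **Attribution.** The inflation depends on where the triggering bleed is counted. Since the bleed day is Day 0 of the reset schedule, a programmer could place it in the new level, and rejection would then be about 2%. This stands as a condition on the finding. The natural reading goes the other way: SAP 8.1.1 counts bleeds during the final dose, and the new dose starts the day after.

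**Eligibility.** SAP 3.4.1 asks for "History of frequent spontaneous bleeding episodes" with a historical ABR of at least 12. If that means 12 spontaneous bleeds and historical rates persist, the 9 + 3 and 6 + 6 cases would be ineligible and most subjects would lie above the null, where inflation fades. A reader might infer from the table that this trial has a one-third to one-half chance of a false positive. The documents do not support that, because they do not give the true rates. But SAP 8.1.1 reads 12 as total bleeds and as the minimum for each subject, and a 2.5% test has to hold at its own boundary.

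**Visibility.** A reader might also infer that the plan hides bleeding. It does not. Bleeding that requires escalation falls under the primary objective (Protocol 3.1) and is a secondary endpoint (SAP 4.2). The number of subjects escalated is reported (Protocol 9.4.1). SAP 8 and 8.2.1 give overall summaries, breakthrough bleeds and bleeding days across Part 2. None of these corrects the primary p-value.

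**Sensitivity analyses.** SAP 8.1.2 changes only the population. The repeated-measures model in Appendix I leaves its time variable undefined, and nothing shows that it removes the selection.

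**Endpoint.** Final-dose ABR is the protocol's own endpoint in a small Phase 2 study meant to find each subject's dose. That is a good reason to keep reporting it. It does not give the comparison with 12 a 2.5% error rate.

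**Conclusion.** The point holds, with conditions. Suppose the triggering bleed is counted where it occurred, bleeds follow a common Poisson rate and the test is corrected for exposure. An inert product at a true total of 12 then shows a final-dose ABR of about 6.2-7.4 and is declared effective in about 34-57% of trials when 50-100% of bleeds are spontaneous, and in about 24% (ABR about 8.1) at 40%. That ABR is close to the rate of 6 on which the trial was powered. Rejection drops to about 27% at 12 + 2, 9% at 12 + 4 and 2% at 12 + 6 or 18 spontaneous. The downward bias remains there: a true 18 is reported as about 12 to 13. The p-value and the final-dose ABR can mislead even though the excluded bleeds appear elsewhere in the report.

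**What to change.** 1. Keep final-dose ABR as the protocol endpoint, but report it as an estimate conditional on the escalation rule. Do not present its comparison with 12 as a test with 2.5% error.
2. State in SAP 8.1.1 that the triggering bleed counts at the level where it occurred and is included in the pooled analysis.
3. Prespecify the pooled analysis (all Part 2 bleeds, triggering bleeds included, over all Part 2 exposure, against 12 a year) as the confirmatory comparison, or at least alongside the final-dose estimate. Settle the choice left open in Protocol 9.4.2 and declare it in SAP section 14.
4. Add an overdispersion-robust interval. Pooled type I error is about 2% under a common Poisson rate but about 5-7% under an assumed gamma variance of 0.5-1.0 between subjects, so pooling alone does not guarantee 2.5%.
5. If the final-dose question is still tested, take the critical value from a simulation of the escalation rule at a total of 12, over the observed exposure and the plausible range of spontaneous/traumatic splits, and use the most conservative value. For 12 × 50 days under a common Poisson rate it is 2 bleeds if all are spontaneous (type I error 1.5%), 3 at 9 + 3 and 5 at 6 + 6, so no single number should be fixed in advance.
6. Define the time variable in Appendix I, and correct the missing exposure term in equation (1) as a separate matter.

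**Cost.** No new data and no change to any dosing or escalation rule. Pooling answers a different question: it includes titration bleeds and gives a less favourable ABR. Its power is about 84-89% at a flat rate of 6 (4.5 + 1.5 and all spontaneous), but 57%, 38% and 11% for assumed rates of 12/8/4/2, 12/9/6/3 and 12/12/12/3 at 30/60/90/120 µg/kg. The cut-off of 2 has 62% power at a flat 6 if all bleeds are spontaneous and 29% at 4.5 + 1.5; in the three dose-dependent cases it has 77%, 58% and 36%.

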### 3.5 DETERMINATION OF SAMPLE SIZE

With a total of 12 subjects and assuming a null hypothesis of an ABR of 12, then if the true ABR for MarzAA is 6 or less, with a one-tailed 2.5% significance level there is near 100% power to demonstrate this using a one sample Poisson test of the null hypothesis. Even if only 6 subjects were available to be pooled for this analysis, the power would still be in excess of 99%. Thus, a sample of 12 subjects is expected to provide sufficient power for the primary endpoint analysis in this study.

Twelve subjects were chosen to increase the size of the safety data set.

If a subject does not complete the study as defined in the protocol (i.e., before receiving study drug for 50 days at the same dose level) another subject will need to be enrolled in replacement.

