**Statistical Analysis Plan**

Catalyst Biosciences, Inc. Protocol # MAA-201

Version 2.0

Syneos Health #1009647

In order to compare ABR (spontaneous and total) during part 2 when on final MarzAA dose level with the actually recorded historical data, a Poisson regression model using PROC GENMOD procedure will be used with the ABR as the dependent variable, intercept as the independent variable and log e transformed of 12 will be used as offset variable. An example SAS code has been provided in [Appendix I](#).

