**Version 2.0**

**Syneos Health #1009647**

## **APPENDIX I EXAMPLE SAS CODE**

**Poisson regression model for primary efficacy endpoint:**

```
PROC GENMOD DATA = bleed;  
MODEL abr = / DIST = poi LINK = log PRED OFFSET = <ln (12)>;  
EXACT intercept/ESTIMATE = parm ONESIDED ALPHA = 0.025;  
RUN;
```

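### The primary test has no valid exposure term: the critical-count rule always rejects, and the SAS model has a type I error of about 24% instead of 2.5%

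*SAP*

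**What the plan says.** SAP Section 8 fixes the level: "The primary efficacy endpoint will be tested inferentially using a one-sided test with 2.5% significance level". Section 8.1.1 sets the null value: "The pre-defined rate is assumed to be 12 bleeds in total (i.e. one bleed per month"). It annualises each subject's bleeds as bleeds divided by months, times 12, where months are exposure days at the dose level divided by 30.5.

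The same section then gives two ways of doing the test.

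- **Critical count.** "Let n be the number of subjects, we can calculate the critical point" N_crit, defined as the largest integer whose cumulative probability under a Poisson mean of n x lambda0 does not exceed alpha. The decision follows: "If the total number of bleeds during the final MarzAA dose for all subjects is less than" N_crit, the null hypothesis is rejected.
- **Regression.** "a Poisson regression model using PROC GENMOD procedure will be used with the ABR as the dependent variable", with an intercept only and log 12 as offset. Appendix I codes it as "MODEL abr = / DIST = poi LINK = log PRED OFFSET = <ln (12)>", with a one-sided exact test of the intercept at 0.025.

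On follow-up, Protocol 4.2 defines completion as "including treatment at the same dose level for 50 days". On power, SAP 3.5 says that "if the true ABR for MarzAA is 6 or less, with a one-tailed 2.5% significance level there is near 100% power" with 12 subjects, and more than 99% with 6.

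**The concern.** In the critical-count rule, the threshold is on a yearly scale and the statistic is a raw count over about 50 days. No exposure time enters formula (1), so the two sides are not comparable.

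The regression fails in a different way. Annualising uses exposure and puts the mean on the yearly scale. The model then takes a rate in which each bleed counts about seven times as though it were that many independent bleeds. It also gives every subject equal weight, whatever his exposure.

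This is the trial's primary test, and SAP 8.1.2 repeats it in the modified ITT and per-protocol populations, so those sensitivity analyses inherit the fault. The two versions can also disagree on the same data, and the SAP does not say which decides.

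**Working it through.** **Inputs.** One-sided alpha 0.025 (SAP 8); lambda0 = 12 per year (SAP 8.1.1); n = 12, alternative ABR 6 (SAP 3.5); 50 days at the final dose (Protocol 4.2); year of 30.5 x 12 = 366 days (SAP 8.1.1). All probabilities are exact Poisson. The critical value c is the largest integer with P[Poisson(mu0) <= c] <= 0.025.

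**1. The plan's power claim.** It reproduces only if each subject contributes a full year.

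| Subjects | mu0 | c | Attained alpha | Power at ABR 6 |
|---|---|---|---|---|
| 12 | 12 x 12 = 144 | 120 | 2.27% | > 99.99% |
| 6 | 6 x 12 = 72 | 55 | 2.24% | 99.88% |

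So the plan's own figures read lambda0 as 12 per subject-year, with one year per subject.

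**2. Critical-count rule as written.** Expected bleeds at ABR 12 over 50 days are 12 x 12 x 50/366 = 19.67. The rule rejects when the raw total is below 120. P[Poisson(19.67) <= 119] is 1 for practical purposes (complement about 1e-52). It still rejects about 98% of the time at a true ABR of 60, and 50% at about 73.

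**3. Regression as coded.** One bleed in 50 days becomes 366/50 = 7.32 on the ABR scale.
- The summed ABR has mean 7.32 x 19.67 = 144, as the model assumes. Its variance is 7.32² x 19.67 = 1054, where the model assumes 144, a ratio of 7.32.
- The documents do not say how an exact Poisson procedure handles non-integer responses. Taking the integer part of the sum, 16 bleeds give 16 x 7.32 = 117.1, inside the cut-off of 120; 17 give 124.4, outside it. The model therefore rejects at 16 or fewer.
- Type I error is P[Poisson(19.67) <= 16] = 24.3%. Rounding each ABR, or using a Wald test, also gives 24.3%. With a 365-day year it is 23.9%; with 53 days each, 23.7%; with 6 subjects at 50 days, 23.5%.

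If the true untreated rate lies above the boundary, the regression's false-positive rate falls:

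| True ABR | 12 | 13 | 14 | 15 | 18 |
|---|---|---|---|---|---|
| P(reject) | 24.3% | 14.7% | 8.4% | 4.5% | 0.5% |

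**4. Test with exposure in the Poisson mean, 50 days each.**

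| Subjects | Year (days) | mu0 | Reject if bleeds <= | Attained alpha | Power at ABR 6 |
|---|---|---|---|---|---|
| 12 | 366 | 19.67 | 10 | 1.29% | 60% |
| 12 | 365 | 19.73 | 11 | 2.45% | 71% |
| 6 | 366 | 9.84 | 3 | 1.17% | 28% |

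With the 366-day year, a cut-off of 11 for 12 subjects gives 2.512% and just fails.

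**The case against.** The strongest reply is that the critical-count paragraph is not what will be run. SAP 8.1.1 says the test uses an exact Poisson regression in SAS 9.4, Section 14 confirms SAS 9.4, and Appendix I labels the GENMOD code as the primary model. On that reading the operative error is 24%, not 100%, and it is wrong to say that the code ignores exposure. Both statements are fair. They set the size of the error in practice; they do not bring it near 2.5%. The critical-count rule remains in the SAP as the formal statement of the decision.

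A second reply is that lambda0 in formula (1) is a generic symbol. If it meant expected bleeds over actual follow-up (12 x 50/366 = 1.64 per subject), the rule would hold its level. The SAP never says so, it fixes the rate at 12, and its stated power needs the yearly reading. If the total were instead meant as summed ABRs, the result is the 24% case.

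A third is that entry requires a historical ABR of at least 12, so untreated rates may well exceed the boundary and the 24% would then be too high. That is true of the regression, as the table shows. But the SAP's null hypothesis is ABR >= 12, and size at 12 is what the 2.5% level promises. The critical-count rule still rejects essentially always at those rates.

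Two smaller points also stand. The strict inequality against N_crit is slightly conservative (1.83% instead of 2.27% on the yearly scale), so it is a wording slip and not part of the harm. And the documents describe a 12-subject open-label Phase 2 study and do not call this test confirmatory.

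**Conclusion.** The concern holds. Followed literally, the critical-count rule rejects with certainty when the true ABR is 12, and would do so at any plausible rate. The regression in SAP 8.1.1 and Appendix I has a type I error of about 24% at ABR 12, nearly ten times the nominal level.

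These figures assume 12 subjects with 50 days each at the final dose, Poisson bleeds at a common rate, and lambda0 = 12 per subject-year, an inference from the SAP's stated rate and its power figures.

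They leave out a separate problem: a subject stays at one of the first three dose levels only if free of spontaneous bleeds after the fifth dose, so final-dose counts are selected to be low. In a simulation with no drug effect, ABR 12, 50 days per level and all bleeds spontaneous, the exposure-adjusted test still rejected about 57% of the time and the Appendix I code about 93%. Correcting exposure is therefore necessary, but on its own does not deliver 2.5%.

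**What to change.** - **Model.** Use observed bleeds at the final dose as the response: `MODEL bleeds = / DIST=POI LINK=LOG OFFSET=logexp`, where `logexp = log(12*exposure_years)` is computed beforehand. Keep the EXACT statement. Change the matching text in SAP 8.1.1.
- **Critical count.** Replace n x lambda0 by 12 x T, where T is total exposure in years over all subjects. Reject when total bleeds are less than or equal to the largest k with P[Poisson(12T) <= k] <= 0.025. State that this and the exact regression are one and the same test.
- **Year length.** Fix it in the text, because the cut-off for 12 subjects at 50 days is 10 with the SAP's 366-day year and 11 with 365 days.
- **Power.** Restate it in SAP 3.5, the protocol synopsis and Protocol 9 and 9.2 for the planned exposure: about 60% with 12 subjects and 28% with 6 at ABR 6, using the 366-day year.

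Exposure by dose level is already defined in SAP 12.1, so no new data are needed. The cost is SAP wording, two lines of code and a revised sample-size paragraph. The selection caused by escalating after bleeds needs its own remedy.
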